Study Endpoints Primary, Secondary and Mechanistic	Primary outcome: Change in symptom burden over time (12 weeks) as measured by Dialysis Symptom Index (DSI) severity score. Secondary outcomes: Change in generic health-related quality of life over time (12, 26, 52 weeks) as measured by EuroQol 5D-5L and EuroQol visual analogue scale Change in: modified symptom burden (modified DSI severity score); time for recovery post-HD; frailty status (Fried criteria); physical activity level (accelerometer and Godin-Shephard Leisure Time Physical Activity Questionnaire); exercise capacity (Incremental Shuttle Walk Test); self-

	efficacy for exercise (Self-Efficacy for Exercise Questionnaire; hospitalization rate (number hospital days admitted/patient year); all cause 1 year mortality
Brief Summary of Analysis	Sample size : The following assumptions were made: alpha 0.05; power 0.80; 30% dropout and 25% absolute difference in proportion of individuals in whom DSI severity score decreases by 7 points or more (minimal clinically important difference). Therefore, assuming a baseline symptom prevalence of 50% of individuals in each study group, 150 patients (75 in each arm) will be randomized and we will be able to detect a 25% reduction in the primary outcome.
	Primary analysis : Intention-to-treat, available-case basis, in the intervention versus control arm, using Chi-square test and logistic regression for categorical outcomes and t-tests/MannWhitney U for continuous outcomes.
	Secondary outcomes : Descriptive statistics, Kaplan Meier analysis, Poisson regression and linear mixed modeling and will be used as appropriate.

SCHEMATIC OF THE STUDY DESIGN

Enrolment and consent: Once informed consent is obtained, the Dialysis Symptom Index (DSI) will be administered to all participants. Those who score 0 on the DSI (no symptoms) will be deemed ineligible for the study

Randomization: To avoid bias, randomization will be performed following the baseline assessment.

Intervention phase: Participants in "intervention" group will receive study intervention during this time.

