- a. Using total active minutes per day as measured by multi-directional accelerometry. One week before each study assessment visit, participants will wear Actical Physical Activity MonitorsTM (Philips Respironics, Bend, OR) on their dominant hip during waking hours for a period of 7 days with 15 second epochs. This technique is considered the gold standard for physical activity assessment. ⁶⁰ During any cycling exercise, participants will wear the device on their dominant ankle. Valid files for analysis will require at least 3 days with a minimum of 8 h of wear time per day. Total active minutes will be calculated by summing the minutes per day spent in light intensity and moderate-to-vigorous physical activity (MVPA) based on pre-specified activity count cut points. ^{61, 62} Accelerometry is included to adjust for physical activity in the control group and address potential contamination.
- b. Using the Godin-Shephard Leisure-Time Exercise Questionnaire, which uses frequency and intensity of leisure time activity to calculate a total leisure time activity score. (REF)

The total leisure time activity score has been validated against measures of physical fitness and objective measures of physical level activity collected by accelerometry in individuals with chronic disease. ^{63, 64}

- **4.** Change in Exercise Capacity from baseline to 12, 26 and 52 weeks as measured by Incremental Shuttle Walk Test (ISWT) (Appendix B-3). Total distance is recorded as individuals walk 10-meter lengths to self-reported exhaustion at pre-programmed progressively increasing speeds as indicated by recorded beeps. ISWT has been used repeatedly in elderly and CKD populations, minimal clinically important differences have been established in chronic disease populations and results are correlated with other measures of exercise capacity. 65,66-68 ISWT was chosen to objectively measure physical function because standardized walking speeds at each stage make it less subject to measurement error due to variable participant effort than other similar tests.
- **5.** Change in frailty status from baseline to 12, 26 and 52 weeks assessed using the Modified Fried Criteria. ^{69,70} Defined as the presence of ≥ 3 criteria of the following criteria: weight loss; exhaustion; slowness; low physical activity; and weakness. As a predictor of adverse outcomes and associated with symptom burden, it is important to determine if frailty status can be modified through exercise

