9.2 Sample Size and Power

Based on the limited literature published in this area, we expect an absolute difference of 25% between the intervention and control groups in the proportion of individuals in whom DSI severity score decreases by 7 points or more over time.

We predict DSI score will decrease in 50% of the intervention group and 25% of the control group at 12weeks (baseline prevalence of symptoms assumed to be 50%). A sample size of 58 patients in each arm will allow us to detect this difference with 80% power (alpha 0.05). We conservatively anticipate 30% dropout.⁸³ Therefore, a target sample size of 150 participants (75 participants per study arm) is proposed.

This sample size will allow us to detect a 7-point difference in mean change in DSI severity score using standard deviation of 16 with 80% power and alpha 0.05. This sample size (n=75 in each arm) will also provide 80% power with 0.05 alpha to detect a 12-point difference between groups in mean change in HRQOL measured using EQ-VAS (considered clinically important difference in other chronic diseases)⁸⁵ and a 30% absolute difference in proportion of individuals endorsing deficits in each domain of EQ5D-3L over time assuming 50% baseline deficit and development of new deficits in an additional 10% of the control group and a reduction in deficits in 15% of the intervention group.

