9.3 Description of Statistical Methods

9.3.1 Primary Outcome

Developed in consultation with a statistician ([name], Chronic Disease Innovation

Centre) familiar with RCTs and our study outcomes, analysis will be performed in an intention-to-treat manner on a case available basis. Change in DSI severity score from baseline to 12 weeks will be compared between groups by independent two-tailed t-test or Mann-Whitney U test depending on distribution and using generalized linear mixed models with study timepoint as a random effect and adjusted for baseline DSI score. In a subgroup of individuals whose baseline DSI score is >7, the proportion of individuals whose DSI severity score has improved by 7 or more points from baseline to 12 weeks will be compared between groups at each study time point using Chi-square test.

Multiple logistic regression will be performed to determine predictors of a >7 point change in DSI severity score over time and adjusted for time varying confounders using a marginal structural model. Interaction terms for sex and baseline DSI score will also be inputted into the model. Although study group will be the primary predictor in this model, other key predictors of symptom burden (including baseline DSI score, diabetes status, ischemic heart disease (IHD), age, gender, race, smoking status, serum albumin level, hemoglobin, baseline physical function, physical activity level and interaction terms for gender/intervention and baseline DSI score/intervention) will also be tested in a step-wise manner.

If **missing outcome data** is greater than anticipated (25%) we will impute them according to current FDA/NAS/NRC recommendations using multiple imputation with chained equations ⁸⁶⁻⁸⁸. Specifically, multiple imputation creates 20-40 complete datasets with plausible values from the model-based predictive distributions, and pooled estimates and standard errors are obtained through the use of Rubin's combining rules. These models are predicated on the assumption that the data are missing at random (MAR). Finally, the robustness of the inferences about treatment effects to violations of the MAR assumptions will be evaluated through a sensitivity analysis ⁸⁸.

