9.3.3 Secondary Outcomes and Analyses

We will repeat the primary outcome analyses that compared change in DSI from baseline to 12 weeks between groups, instead looking at change from baseline to 26 weeks and 52 weeks.

Change in EQVAS over time will be compared between study groups using Student's T-test. As well, we will compare the difference in proportion of individuals who develop new deficits (score of 2 or 3) in each domain of the EQ5D-5L over time. The degree to which change in symptom burden correlates with change in EQVAS will be assessed using Spearman and Pearson's correlation coefficients as indicated based on distribution of the data. Change in all other secondary outcomes over time will be compared between groups using the appropriate parametric and non-parametric statistical tests depending on data type and distribution. Bonferroni adjustments will be made for secondary outcomes to adjust for multiple study timepoints. Hospitalization will be analyzed using Poisson regression. For all analyses, two-sided p < 0.01 will be statistically significant. Statistical analysis will be performed using SAS 9.3 (Carey, NC).

We will validate the Godin Shepard Leisure-Time Exercise Questionnaire using accelerometry data. Correlation between Godin Questionnaire Score and active minutes (light, moderate and moderate-vigorous activity) measured by accelerometry at each study assessment time point will be assessed using Pearson or Spearman correlation depending on distribution of the data. Internal consistency of the Godin questionnaire will be assessed using Cronbach alpha and Intraclass Correlation Coefficient. In those individuals in which active minutes measured using accelerometry did not change between assessment periods (change of less than 10% from baseline), test re-test reliability of the Godin Questionnaire will be assessed using Kappa statistic. Responsiveness will be modelled using linear regression with Godin questionnaire score as the primary predictor of active minutes measured by accelerometry. Additional predictors including sex, age, diabetes and other comorbidities will be added to the model as sample size will allow.

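### One logistic model is asked both to search for predictors and to estimate the group effect on the responder outcome, and its specification does not protect the randomised comparison

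*Combined protocol and SAP*

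**What the plan says.** The synopsis (Brief Summary of Analysis) describes the primary analysis as intention-to-treat "using Chi-square test and logistic regression for categorical outcomes", with t-tests or Mann-Whitney tests for continuous outcomes. The binary form of the primary outcome in 4.2.1 is a fall of at least 7 points in DSI severity score from baseline to 12 weeks.

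Section 9.3.1 first sets out comparisons between groups: a t-test or Mann-Whitney test on change in DSI, a mixed model adjusted for baseline DSI, and a Chi-square test of the responder proportion among patients whose baseline DSI is above 7. It then describes one multiple logistic regression. Its stated aim is to find predictors of response, but study group is its main predictor. The model is to be "adjusted for time varying confounders using a marginal structural model". Besides group it has 13 candidate terms, which "will also be tested in a step-wise manner":

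- 11 covariates: baseline DSI, diabetes, ischaemic heart disease, age, gender, race, smoking, albumin, haemoglobin, baseline physical function and physical activity level;
- 2 interactions: gender by intervention and baseline DSI by intervention.

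Section 4.2.3, item 3a, adds: "Accelerometry is included to adjust for physical activity in the control group and address potential contamination".

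The plan does not name the time-varying confounders, and it gives no weight model, selection rule or coding for the interactions. It does not say when the physical activity covariate is measured.

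**The concern.** A search for predictors and an estimate of a randomised effect need different models. Four features of this one bear on the group coefficient.

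1. **Time-varying adjustment.** Nothing that happens after randomisation can confound a randomised group, but it can be a consequence of the programme. A marginal structural model can answer a question about adherence or dropout, but the plan links it to neither.
2. **Physical activity.** Section 4.2.3 makes it an outcome that the programme is meant to change. If measured during follow-up, it is a plausible mediator.
3. **Interactions.** With group interactions in the model and no centring, the group coefficient is the effect at a baseline DSI of 0 in the reference gender. Section 5.2 excludes patients who score 0.
4. **Stepwise selection.** There are few responders for the number of candidate terms.

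This matters because, within 9.3.1, the logistic model is the only responder analysis not confined to baseline DSI above 7, whereas eligibility requires only a DSI above 0. The trial is sized on the responder outcome. An adjusted odds ratio that disagreed with the simple tests for technical reasons would leave no prespecified rule for which to believe.

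**Working it through.** **Inputs.** Section 9.2: "We predict DSI score will decrease in 50% of the intervention group and 25% of the control group at 12weeks"; alpha 0.05, power 80%, 58 per arm; "We conservatively anticipate 30% dropout"; 75 randomised per arm. Section 4.2.1: pilot SD 30. The documents give no mean baseline DSI and no share of effect carried by activity, so both are assumed below. All power figures use two-sided 0.05.

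**The plan's own figure.** Pooled proportion 0.375:

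n = [1.96 × √(2 × 0.375 × 0.625) + 0.8416 × √(0.25 + 0.1875)]² / 0.25² = 57.7, so 58 per arm. This reproduces.

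**Responders per term.** 75 × 0.70 = 52.5, so about 52 completers per arm. Responders: 52 × 0.50 + 52 × 0.25 = 39. With 13 candidates plus group, 39 / 14 = 2.8 responders per term.

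**Simple model.** Odds ratio (0.5/0.5) / (0.25/0.75) = 3.0; log 1.10. Variance = 1/(52 × 0.5 × 0.5) + 1/(52 × 0.25 × 0.75) = 1/13 + 1/9.75 = 0.179; SE 0.42. Power ≈ Φ(1.10/0.424 − 1.96) = 74% by this approximation and about 76% by simulation.

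**Activity measured after baseline.** Take a log odds ratio of 1.1 and let a share s run through activity. Conditioning on activity leaves exp[1.1 × (1 − s)]. In the simulation the programme raised activity by 0.8 SD. Compare within rows, because the total odds ratio also changes with the set-up.

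| Share s (assumed) | exp[1.1(1 − s)] | Simulated, total to adjusted |
|---|---|---|
| 25% | 2.28 | 2.93 to 2.29 |
| 50% | 1.73 | 2.70 to 1.73 |
| 75% | 1.32 | 2.47 to 1.30 |
| 100% | 1.00 | 2.26 to 1.00 |

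A separate simulation at 50% gave 2.85 to 1.74. With no mediation, but an unmeasured common cause of activity and response, the odds ratio still fell from 2.63 to 2.06.

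**Marginal structural weights.** Weights for group built from follow-up activity (50% mediated) gave an odds ratio of 1.62 against about 2.7. Weights built from a baseline covariate lay between 0.998 and 1.002 and did no harm. The damage comes from post-randomisation information, not from weighting as such.

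**Uncentred interactions, both kept, no true interaction.** The variance of the group coefficient is multiplied by about 1 + (mean DSI/SD)² + 1, where the last 1 is 0.5²/0.25 for an evenly split gender.

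| Mean, SD of baseline DSI | Factor | SE | Approximate power |
|---|---|---|---|
| 40, 25 (assumed) | 4.56 | 0.90 | 23% |
| 20, 30 | 2.44 | 0.66 | 38% |
| 40, 30 | 3.78 | 0.82 | 27% |
| 60, 30 | 6.00 | 1.04 | 18% |

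Simulations at mean 40, SD 25 gave 19% to 21%. With centred terms power was about 75%, and with null interactions dropped about 71%.

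The meaning of the coefficient also shifts. If the effect rises by b log odds per DSI point, the coefficient at DSI 0 is exp(1.1 − 40b): 2.0, 1.3 and 0.9 for b = 0.01, 0.02 and 0.03. The overall odds ratio is about 3.0 in each case.

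**Stepwise selection, group forced in.** Under the null, the group term was rejected in 7.2% of 500 runs, against 5.0% unadjusted. With a true effect and no mediator, the median odds ratio was 3.03 against 2.89. With activity as a 50% mediator among the candidates, it was 1.79 against 2.72, and power fell from 71% to 28%.

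**The case against.** The strongest reply is that the regression is introduced as a search for predictors and follows three group comparisons that are free of these problems. That is right about those comparisons. It does not settle the matter, because the synopsis puts logistic regression in the primary analysis and 9.3.1 gives group the leading role.

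Four stronger readings are tempting, and the documents do not support them.

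- **That the intention-to-treat effect is lost.** The t-test or Mann-Whitney test, the mixed model and the Chi-square test do not depend on this regression.
- **That the plan commits to adjusting for a mediator.** Section 9.3.1 does not time physical activity. Section 9.3.2 calls baseline activity a potential confounder, which favours a baseline reading. The accelerometry sentence in 4.2.3 favours a follow-up reading but names no model.
- **That power will fall to about 20%.** This needs interactions that are both uncentred and kept. The plan states no coding, and under stepwise testing null interactions would usually drop out.
- **That stepwise testing inflates the error rate to 19%.** One simulation gave that figure for any of three group terms being significant. Three independent tests already give 1 − 0.95³ = 14%, so most of it is multiplicity.

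A marginal structural model is also not wrong in itself: it weights rather than conditions, and could serve the on-protocol analysis in 9.3.2 or the expected dropout. What stands is that no such question or weights are defined.

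**Conclusion.** The point holds for the logistic model only. As written, its group coefficient is not tied to the randomised effect on the responder outcome, and the plan does not exclude versions in which it misses that effect badly.

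The size depends on choices left open. If follow-up activity enters and carries half the effect, the odds ratio falls from about 2.9 to 1.7. If uncentred interactions stay in, power falls from about 76% to about 20%, or 18% to 38% by approximation at the pilot SD of 30 and assumed means of 60 down to 20. If only baseline covariates are used and interactions are centred or dropped, the loss is small, and stepwise selection remains a minor fault. These figures rest on 52 completers per arm, response of 50% and 25%, and the assumed mediation shares and DSI means.

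The powers use the 0.05 level of 9.2. Section 9.3.3 says "For all analyses, two-sided p < 0.01 will be statistically significant"; at 0.01 even the simple comparison has about 52% power with 52 per arm. That conflict is a separate matter. Since the other comparisons are sound, this should be corrected but does not undermine the trial.

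**What to change.** - **Treatment effect on the responder outcome:** in 9.3.1, specify a logistic model with group, baseline DSI and at most a few baseline covariates fixed in advance. Use no stepwise selection and no post-randomisation covariates or weights. Define response as in 4.2.1 (7 points or more; the regression now says more than 7).
- **Interactions:** test gender and baseline DSI in separate, exploratory models.
- **Predictor search and marginal structural model:** keep both as exploratory, the latter only for a stated adherence or dropout question with its weights defined.
- **Section 4.2.3, item 3a:** keep accelerometry to describe contamination, and state that activity measured after baseline does not enter the main effect model.

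The cost is a small amount of rewording and one extra simple model. No visit, measurement or sample size changes.

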9.3.4 Demographic Data

Statistical presentation for baseline and demographic characteristics will be reported. Specifically, we will compare baseline descriptive variables between study groups using independent two-tailed t-test or Mann Whitney U test for continuous variables and Chisquare test for categorical variables, as appropriate. Similarly, individuals who complete the study protocol will be compared to those who do not. As per the latest FDA/NRC/NAS guidelines for the treatment of missing data in clinical trials, the same data will be tabulated

for patients with incomplete records. If missing outcomes are greater than 25%, multiple imputation techniques will be used as per FDA recommendations.⁸⁸

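### Multiple imputation is used only above 25% missing outcomes, so below that level the 12-week responder comparison rests on available cases, although the plan expects 30% dropout

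*Combined protocol and SAP*

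**What the plan says.** The default is stated twice. In section 9.3.1, "analysis will be performed in an intention-to-treat manner on a case available basis". The analysis summary in the synopsis agrees: "Intention-to-treat, available-case basis, in the intervention versus control arm".

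Imputation is a contingency. Section 9.3.1 says that if missing outcome data "is greater than anticipated (25%) we will impute them", by chained-equations multiple imputation. Section 9.3.4 repeats the rule: "If missing outcomes are greater than 25%, multiple imputation techniques will be used as per FDA recommendations". The same paragraph of 9.3.1 gives the number of imputed datasets (20 to 40), pooling by Rubin's rules and the missing-at-random (MAR) assumption. It closes with a sensitivity analysis to violations of MAR, for which it gives no method.

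The expected loss is stated differently elsewhere. Section 9.2: "We conservatively anticipate 30% dropout". The synopsis lists "alpha 0.05; power 0.80; 30% dropout and 25% absolute difference in proportion of individuals in whom DSI severity score decreases by 7 points or more".

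The plan does not say whether 25% is counted overall, per arm or per visit. Nor does it say whether the imputed result replaces the available-case result or stands beside it.

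**The concern.** Three things are at stake.

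- **The level called anticipated.** Sections 9.3.1 and 9.2 give different figures, and nothing reconciles them. If the loss is what 9.2 plans for, the fallback becomes the expected analysis.
- **The threshold itself.** The risk of bias depends on who is missing and in which arm. It does not begin at 25%. An overall count also cannot see an imbalance between arms.
- **What happens below the threshold.** The 12-week responder proportion defines the primary outcome in section 4.2.1 and drives the sample size in 9.2. A chi-square test on available cases drops every participant without a 12-week Dialysis Symptom Index (DSI) score. It makes no use of that person's enrolment, baseline or later DSI, all of which the schedule in section 7.3 collects. The check on departures from MAR may also lapse, since it is described only within the imputation paragraph.

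**Working it through.** **Inputs.** 150 randomised, 75 per arm; responders 50% against 25%; 80% power; alpha 0.05; 30% dropout (all section 9.2). Imputation trigger above 25% (sections 9.3.1 and 9.3.4).

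**1. The plan's own sample size.** With pooled variance, two-sided and no continuity correction, the mean proportion is 0.375 and

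n = [1.96 × √(2 × 0.375 × 0.625) + 0.8416 × √(0.50 × 0.50 + 0.25 × 0.75)]² / 0.25² = (1.342 + 0.557)² / 0.0625 ≈ 57.7, so 58 per arm.

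This reproduces the stated 58. Going from 58 to 75 per arm allows for a loss of 1 − 58/75 = 22.7%. The documents therefore contain three levels of expected loss: 22.7% (implied), 25% and 30%.

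**2. Where the trigger lies.** If counted over all randomised, 0.25 × 150 = 37.5, so imputation starts at 38 missing. Up to 37 missing outcomes (37/150 = 24.7%) are left unimputed. At the 30% of section 9.2, the expected number missing is 0.30 × 150 = 45, which is above the trigger.

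**3. How often the trigger fires.** Assume that 30% dropout means 30% missing 12-week outcomes, that participants go missing independently, and that the count is over all 150. Then the number missing, X, is Binomial(150, p):

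| True missing fraction p | P(X ≥ 38) |
|---|---|
| 20% | 0.066 |
| 25% | 0.494 |
| 30% | 0.911 |

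**4. The threshold and imbalance between arms.** As an assumed split, let 27 of 75 be missing in the intervention arm (36%) and 9 of 75 in control (12%). The total is 36 of 150, or 24%, and an overall trigger does not fire. The example shows only that the rule does not detect imbalance. It says nothing about the direction of any bias.

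**5. Which analyses use partial data.** Section 9.3.1 applies the generalized linear mixed model, adjusted for baseline DSI, to change in the DSI severity score. The responder proportion is compared by chi-square, which needs a 12-week score. The mixed model therefore leaves the responder comparison as it is.

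**The case against.** **Dropout and missing outcomes need not be the same quantity.** This stands. Section 2.3.1 keeps participants under observation after the intervention is stopped for a monitored event. Section 5.4.2 asks those who leave early for final assessments, and Appendix 5 allows the DSI to be collected by phone, email or mail. Missing outcomes could therefore be fewer than dropouts, and 9.2 calls its 30% conservative. A reader might infer that 25% and 30% flatly contradict each other. The documents do not establish that; they leave the two figures unreconciled, with the 30% applied to the 12-week sample size.

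**The rule is set in advance.** Also true. It depends on the missing fraction, not on the treatment effect, and section 7.3.2 blinds the statistician. A reader might infer that the analyst is free to choose between two primary results, but the text does not support that. What remains open is how the 25% is counted and whether imputation replaces or supplements the default.

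**The binomial denominator may be wrong.** The chi-square in 9.3.1 is limited to participants with baseline DSI above 7, so its denominator may be below 150. The probabilities in step 3 hold only for a count over all randomised.

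**A mixed model is planned.** It can use partial follow-up under MAR for the continuous score. It does not cover the responder comparison, and the plan does not name it as the missing-data method.

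**The tempting stronger claim is that available cases overstate the benefit by a known amount.** Suppose 24% are missing in the intervention arm, with completers responding at 50% and dropouts at 25%. The rate over all randomised is then 0.76 × 0.50 + 0.24 × 0.25 = 44%, which is 6 points below the available-case 50%. The documents do not support using this as the size of the problem, for three reasons.

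- It concerns one arm. If control also loses 24% and its dropouts respond at 12.5%, control is 0.76 × 0.25 + 0.24 × 0.125 = 22%. The true difference is 44 − 22 = 22 points against 25 observed, an overstatement of 3. If control dropouts respond at 0%, control is 0.76 × 0.25 = 19%, the difference is 44 − 19 = 25, and the overstatement is zero.
- With nothing observed to explain the gap, the outcomes are missing not at random. MAR imputation would return about 50%, not 44%. Only the sensitivity analysis addresses that case.
- No section says that people who do badly leave the active arm more often.

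**Conclusion.** The concern holds as a weakness in how missing primary data are handled. On the plan's own 30%, the contingency is the expected path, with about 91% probability; at a true 25% it is close to a coin toss. Both figures assume that dropout equals missing 12-week outcomes, that losses are independent and that the count is over all 150. Below the trigger, the responder comparison excludes everyone without a 12-week score, and the MAR sensitivity analysis may not be run. The direction and size of any resulting bias cannot be taken from the documents. The case for change is that a better method is already written into the plan and is withheld by a threshold that gives no protection against bias.

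**What to change.** - Delete the 25% trigger in sections 9.3.1 and 9.3.4. Raising it to 30% would match section 9.2 but make imputation rarer and keep the method dependent on the observed loss.
- Use the chained-equations imputation already specified for the 12-week responder outcome at any missing fraction. Impute the DSI score by arm, using enrolment, baseline, 26-week and 52-week DSI, and then derive response from the imputed score.
- Report the available-case comparison as a sensitivity analysis, and say so in the synopsis as well.
- Run the sensitivity analysis to departures from MAR in all cases, and state its method.

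The cost is a little more analysis work and no new data. The gain has a limit: later DSI scores help only for participants who miss week 12 and then return. For those who leave for good, only the enrolment and baseline scores are available.
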